3. STUDY DESIGN

The present research proposal concerns a randomised feasibility trial, comparing ImCT intervention to psychoeducation. In addition to the between group design, the study also uses a within-group design, where ImCT and psychoeducation is preceded by a four-week baseline condition. Note that during this baseline period and throughout the study, all patients will maintain their regular appointments with their psychiatrist or specialised nurse practitioner, who will prescribe, monitor and adjust mood stabilising medication conform guidelines. The within-group design allows participants baselines to act as their individual control periods with no intervention (Barlow, Nock, & Hersen, 2009; Bonsall, Wallace-Hadrill, Geddes, Goodwin, & Holmes, 2012; Holmes et al., 2016). The study will take place within a specialised centre for bipolar disorders within a large psychiatric hospital (GGzE). All participants start after 4 weeks of baseline with either ImCT or psychoeducation treatment. The duration of the study for participants will be 32 weeks for participants in the ImCT condition and 26 weeks for participants in the psycho-education condition. The difference in duration between the conditions is due to treatment length, that is, 12 weeks weekly 1-hour sessions for ImCT and 6 weeks weekly 2-hour sessions for the psychoeducation treatment. Note that all participants will have had 12 hours face-to-face contact in both conditions.

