6. METHODS

6.1 Study parameters/endpoints

6.1.1 Main study parameter/endpoint

To assess the primary endpoint of this study (1), decrease of mood variability, mood variability is measured using the Affect Lability Score Short Version (ALS-18) (Oliver & Simons, 2004) at baseline (T0), pre- intervention (T1) and post intervention (T2), and at follow-up measurements at 8 (T3) and 16 weeks (T4) after treatment discontinuation in both the ImCT and psychoeducation conditions. The ALS-18 is a self-report scale measuring lability in affect and consists of 18 items. Ratings are made on a 4-point scale with a maximum score of 72. Scores range from A= very characteristic of me (4 points), to D= very uncharacteristic of me (1 point).

In addition we monitor changes in mood variability using the National Institute of Mental Health Life Chart Methodology (NIMH-LCM) Prospective Self-Rating (Denicoff et al., 2000). Participants rate their mood (both mania and depression) on a 9-point Likert scale, ranging from -4 (severe depression, admission required due to severe dysfunction) to 0 (stable mood) to +4 (severe mania, admission required due to severe dysfunction). Daily measurements are calculated during a 4-week baseline prior to start of either ImCT or psychoeducation, during the intervention and until follow up at 16 weeks. This method is advised given that traditional self-report mood ratings over a single time point are scarcely representative of mood variability in bipolar disorder.

6.1.2 Secondary study parameters/endpoints (if applicable):

The following parameters are used for the following secondary objectives:

To assess (2a) level of depression, mania and anxiety and (2b) general functioning and hopelessness (3) number of relapses into mania or depression decline/increase, we administer the following measures:

- Level of depression, using the Quick Inventory of Depressive Symptoms (QIDS-SR) (Rush et al., 2003). The QIDS-SR is a 16-item self-report rating scale in which the nine DSM 5 symptoms of major depression are incorporated. Answers are rated on a four-point Likert scale (0-3). The QIDS-SR is administered weekly throughout the duration of the study.

- Level of mania, using the Altman Self-Rating Mania Scale (ASRM-NL) (Altman, Hedekker, & Peterson, 1997). The ASRM-NL is a 5 item self-report instrument to measure severity of mania symptoms. This is administered weekly throughout the duration of the study.

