8. STATISTICAL ANALYSIS

First, descriptive analyses will be used to establish mean scores, standard deviations and to identify outliers. Missing data from our primary outcome variable, will be listwise deleted. In our other outcome variables, data will only be included if pre- and post-measures are completed.

Second, the data will be checked with respect to violation of assumptions (such as error independency, non-normal distributions) for variance-based models.

Primary outcome variable: mood variability:

To assess if there is a stronger decrease in mood variability in the ImCT intervention condition as compared to the psychoeducation condition, multivariate repeated measures analyses are applied. Dependent variables are the scores on the ALS-18 (baseline, T0; pre-treatment, T1; post-treatment, T2; 8-weeks follow-up, T3; 16-weeks follow-up, T4) with treatment condition (ImCT, psychoeducation) as between subjects variable.

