To assess if (2a) level of depression, mania and anxiety, (2b) general functioning and coping, and hopelessness increase/decline more in the ImCT intervention compared to psychoeducation treatment two types of multivariate repeated measures analyses are applied, both with treatment condition (ImCT, psychoeducation treatment) as independent, between groups variable. In the first type of analyses, the dependent variables are the scores of the weekly measures for depression, anxiety and mania (QIDS-SR, BAI, ASRM). In the second type of analyses, time (T0, T1, T2, T3 and T4) is used as within between subject variables and scores of the same instruments and general functioning and coping and hopelessness (ALS-18, IFE-RIFT, BHS) are used as dependent variables.

To assess if (3) number of relapse into mania or depression decline more in the ImCT intervention compared to psychoeducation treatment Chi-square analyses are applied with as dependent variable number of relapses into mania or depression, using cut-of scores on the ASRM and QIDS-SR during the follow-up period and treatment condition (ImCT, psychoeducation treatment) as between groups variable.

To assess if (4) problematic imagery decreases and imagery characteristics changes more by using the ImCT intervention compared to psychoeducation treatment, comparable to 2a and 2b, two types of multivariate repeated measures analyses are applied, both with treatment condition (ImCT, psychoeducation treatment) as between groups variable. In the first type of analyses, the dependent variables are the scores of the weekly measures of imagery (VAS). In the second type of analyses, time (T0, T1, T2, T3 and T4) is used as within between subject variables and scores of imagery (MICQ-BD and DIS) are used as dependent variables.

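### The multivariate analysis planned for the weekly scores keeps only patients with no missed week, contrary to the plan's own inclusion rule and intention-to-treat statement, and can become uncomputable

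*Combined protocol and SAP*

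**What the plan says.** For the secondary outcomes, section 8 states that "two types of multivariate repeated measures analyses are applied, both with treatment condition" as the between-groups factor. In the first type, "In the first type of analyses, the dependent variables are the scores of the weekly measures for depression, anxiety and mania" (QIDS-SR, BAI, ASRM). A parallel sentence does the same for the weekly VAS-Imagery scores. The second type uses the five occasions T0 to T4.

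Section 6.1.2 sets the frequency; for example, "The QIDS-SR is administered weekly throughout the duration of the study". It says the same of the ASRM, the BAI and the VAS. (Section 2 places imagery measurement at T0-T4 only. I follow sections 6.1.2 and 8, which both have the VAS weekly.) Section 3 gives the length of participation as "32 weeks for participants in the ImCT condition and 26 weeks for participants in the psycho-education condition".

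On missing data, section 8 says of the primary outcome: "Missing data from our primary outcome variable, will be listwise deleted". For the other outcomes, "data will only be included if pre- and post-measures are completed". Weeks missed in between are not mentioned. For the weekly scores no imputation, summary measure or mixed model is described. Section 8 closes by making intention-to-treat the main analysis, with completers as a supplement.

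**The concern.** A classical multivariate repeated-measures analysis needs a full row of scores per patient. With five occasions that is a tolerable demand. With 26 weekly forms, one missed form removes the patient and the other 25 scores. The pre/post rule would admit that patient, but the named method cannot use the row without imputation. The result is a complete-case analysis under an intention-to-treat label.

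The patients who remain would be unusually compliant, and the loss need not be unrelated to outcome. Section 6.4.1 takes patients out of the trial after a relapse admission of more than one week. Deleting incomplete rows would then also discard all their earlier weekly scores.

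The multivariate test has a second requirement: more complete patients than the number of week-to-week contrasts allows for by a small margin. If that is not met, the error matrix is singular and there is no test. At stake is the between-arm use of the weekly data, which cost each patient about 20 minutes a week (section 6.3.3).

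**Working it through.** **The plan's own figures.** Section 4.4 gives 45 per arm for d = 0.6, 80% power and two-sided 0.05. The noncentral t gives power 0.795 at 44 and 0.804 at 45, so 45 reproduces. Allowing for dropout of 1 in 15, 45 x (1 + 1/15) = 48 per arm, 96 in all. The documents state neither a number of weekly variables nor a rate of missed weeks, so the rates below are assumptions.

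**Number of weekly scores.** Baseline 4 + treatment 12 + follow-up 16 = 32 weeks for ImCT; 4 + 6 + 16 = 26 for psychoeducation. At most 26 weeks are common to both arms. Using all 32 is impossible, since no psychoeducation patient could have a full row.

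**Minimum number of complete patients.** 26 weeks give 26 - 1 = 25 within-patient contrasts. With two arms the error degrees of freedom are N - 2. The multivariate time-by-arm test needs N - 2 >= 25, so N >= 27.

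**Expected complete patients, independent misses.** N x (1 - m)^26, where m is the chance of missing any one week:

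| m | (1 - m)^26 | of 90 | of 96 |
|---|---|---|---|
| 1% | 0.770 | 69 | 74 |
| 2% | 0.591 | 53 | 57 |
| 3% | 0.453 | 41 | 43 |
| 4% | 0.346 | 31 | 33 |
| 5% | 0.264 | 24 | 25 |
| 10% | 0.065 | 6 | 6 |

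The expected number equals 27 when m = 1 - (27/N)^(1/26), which is 4.5% for N = 90 and 4.8% for N = 96. At m = 5% the binomial chance of fewer than 27 complete patients is 75% (N = 90) or 62% (N = 96). At 6% it is 98% or 97%.

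**Clustered misses.** In practice some patients miss many weeks and others none. A beta-binomial model with within-patient correlation rho gives, for 90 / 96 patients:

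| rho | m | complete patients |
|---|---|---|
| 0.1 | 10% | 25 / 26 |
| 0.2 | 15% | 24 / 26 |
| 0.3 | 20% | 24 / 26 |
| 0.5 | 30% | 26 / 28 |

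The point at which the test becomes uncomputable therefore moves to roughly 10 to 30%. Below that point many patients are still lost: at rho = 0.2 and m = 10%, 40 of 96 are complete.

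**The case against.** The best defence is that section 8 leaves room for another test. It uses multivariate analyses only where possible and plans to test sphericity, which matters for the univariate repeated-measures test. That test inverts no 25 x 25 matrix: with 25 complete patients it has 23 x 25 = 575 error degrees of freedom. The arm effect averaged over weeks would also compute. This stands, and it limits the impossibility to the multivariate time-by-arm test. It does not help with the loss of patients, because the univariate test in its usual form drops the same rows.

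The 5% threshold is also fragile. The 26 weeks include four before randomisation, and section 4.2 requires successful daily monitoring in that run-in. If the weekly forms were complete then too, 0.95^22 x 96 = 31 patients would remain, above 27. But the criterion covers the daily ratings, not the weekly forms. Nor can high completeness be presumed: section 1 gives better estimates of retention as a reason for the trial.

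Three stronger readings are tempting but not supported.

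- *The model fails whatever the data.* It does not. With 96 complete patients there are 94 error degrees of freedom for 25 contrasts. Failure depends on a missingness rate that the documents do not give.
- *Hypotheses 2a and 4 rest on this analysis alone.* They do not. The second type of analysis refers to the same instruments at T0-T4 (although its bracketed list names ALS-18, the functioning scale and BHS), and section 2 frames hypothesis 2a at T2, T3 and T4. Imagery also has the MICQ-BD and the Dutch imagery survey at T0-T4. Weekly QIDS-SR and ASRM scores feed the relapse comparison as well.
- *The three symptom scales enter together as 78 variables.* The sentence lists three instruments but does not say they form one model. On that reading the time-by-arm test would have 75 contrasts and need 77 complete patients, against 74 of 96 expected at 1% missed. The point does not depend on it.

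**Conclusion.** The concern holds in a conditional form. As written, the weekly analyses keep only patients with no missed week, which conflicts with the pre/post rule and with intention-to-treat, both in section 8. The size depends on assumed missingness: with independent misses and 96 patients, about 57 are complete at 2%, 25 at 5% and 6 at 10%. The multivariate time-by-arm test can become impossible to compute at about 5%, or at roughly 10 to 30% if misses cluster. It assumes one dependent variable per week, which follows from weekly measurement but is not spelled out in section 8.

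The consequence is limited to secondary outcomes. The primary ALS-18 analysis has five occasions and no such dimension problem. What is lost is precision, and possibly freedom from bias, in the weekly comparisons. The loss is greatest for weekly VAS-Imagery, which has no other planned between-arm analysis. The plan should be changed on this point before the data are seen.

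**What to change.** Replace the first type of analysis by one linear mixed model per instrument:

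- **Data:** all available post-randomisation weekly scores of all randomised patients.
- **Baseline:** the mean of the patient's available baseline-week scores, as a covariate only. The baseline weeks must not also appear as outcomes.
- **Fixed effects:** arm, time and arm-by-time, with time indexed by phase (for example, weeks since the end of treatment). Indexing by study week would set psychoeducation follow-up against ongoing ImCT treatment in weeks 11 to 16.
- **Covariance:** a structure stated in advance.
- **Contrasts:** ImCT versus psychoeducation at end of treatment and at 8 and 16 weeks after, named in advance.

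A simpler alternative is to compare each patient's mean weekly score over follow-up between arms, adjusted for the baseline mean. In either case, do not apply the pre/post completeness rule to these outcomes.

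The cost is a change to section 8 and standard software, with no new data or visits. The downside is that the mixed model relies on missing-at-random and on the chosen covariance form.

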6.3.2 Study Assessment Moments

Psychoeducation groups at Centrum Bipolar start once in every six weeks. At four weeks prior to the start of each psychoeducation group the identified participants start with the online measures at baseline (T0), and both daily and weekly online measurements which participants receive by email. Note here that the patients that participate in this study will not wait longer than the patients that choose not to participate. Participants continue to fill in both the daily and weekly online measures for four weeks (the baseline period). After four weeks all participants fill in the measures pre-intervention (T1), and are allocated randomly to either the ImCT or psychoeducation condition, which will then commence. During the intervention period (12 weeks for the ImCT condition, and 6 weeks for the psychoeducation treatment condition) all participants continue to fill in both the daily and weekly online measures. At the end of the intervention, all participants fill in the post-intervention measures (T2) online. Subsequently, all participants continue to fill in both daily and weekly online measures until the end of the study (at follow up at 16 weeks). In addition, participants fill in the post-intervention online measures at follow up at 8 weeks (T3) and 16 weeks (T4) after the end of intervention.

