In addition, to assess reductions in mood variability during the interventions (ImCT, psychoeducation) compared to mood variability during the baseline period, daily mood measures with the National Institute of Mental Health Life Chart Methodology (NIMH-LCM) Prospective Self-Rating of mood (both mania and depression) are assessed, using a case series design, where participants baseline ratings can act as their own control (Arntz, Sofi, & van Breukelen, 2013). Changes in mood variability are investigated using sequence analysis with R-software (package TraMineR version 1.8-10); (Gabadinho, Ritschard, Muller, & Studer, 2011) on the daily scores. Sequences consist of a series of subsequent states (daily scores) and similarities between sequences are calculated with the Optimal Matching technique (OM). Sequences will be defined as day scores from 28 days prior to starting the interventions, until 112 days after the end of interventions. Rather homogenous groups of trajectories (clusters) will be derived from the distance matrix that result from the OM technique. To this end, cluster analysis will be applied. Shannon entropy of transversal state of the scores on each day will be calculated and plotted (Gabadinho et al., 2011). Entropy is a measure of diversity of states (a measure of mood variability) within sequences and varies between zero (all sequences in the same state) to 1 (maximum diversity). To explore the relationship between diversity in states (mood variability) and background characteristics, this longitudinal entropy will be regressed on co-variates (gender, medication). Also, sequences of scores at the start of treatment will be compared to subsequences during treatment and during the follow-up period to explore change over time.

Secondary outcome variables: depression, anxiety, mania, general functioning and coping, hopelessness, number of relapses into mania or depression, and changes in imagery:

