Where possible multivariate analyses are used to analyse differences between groups, and repeated-measures ANOVA to analyse difference within groups. These will be used to minimise the correlations and dependencies between variables. In order to allow for reliable multivariate analysis, assumptions of sphericity are tested. Multivariate analyses between groups (ImCT, psychoeducation treatment) and repeated-measures ANOVA within groups (T0, T1, T2, T3, T4) are used to determine an omnibus effect. If differences are significant, post hoc analyses (mostly independent T-test) will be used to determine individual differences between groups and between points in time. Bonferoni corrections are used to correct for multiple testing.

Intention-to-treat analyses will constitute the central analyses and completers analyses will be done as supplementary analyses.

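### The secondary arm comparisons use no baseline covariate, although four weeks of pre-allocation QIDS-SR, BAI and ASRM scores are collected and would sharpen them

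*Combined protocol and SAP*

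**What the plan says.** Section 6.1.2 sets a weekly schedule; for depression, "The QIDS-SR is administered weekly throughout the duration of the study", and the BAI and ASRM entries say the same. Section 6.3.2 places four of those weeks before allocation: "Participants continue to fill in both the daily and weekly online measures for four weeks (the baseline period"), and then "After four weeks all participants fill in the measures pre-intervention (T1), and are allocated randomly to either the ImCT or psychoeducation condition".

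Section 8 describes two secondary analyses, each with treatment condition as the between-groups variable. For the weekly scales: "In the first type of analyses, the dependent variables are the scores of the weekly measures for depression, anxiety and mania (QIDS-SR, BAI, ASRM"). For the fixed visits: "In the second type of analyses, time (T0, T1, T2, T3 and T4) is used as within between subject variables". The second lists the pre-treatment visits T0 and T1 among the outcome levels. The first does not say which weeks enter.

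After a significant omnibus result, "post hoc analyses (mostly independent T-test) will be used to determine individual differences between groups and between points in time", with Bonferroni correction. The only covariates named anywhere in section 8 belong to the daily-mood analysis: "this longitudinal entropy will be regressed on co-variates (gender, medication"). Baseline otherwise appears in a rule on which data count: "In our other outcome variables, data will only be included if pre- and post-measures are completed". Section 3 has baselines serve as individual controls, but for the within-group design.

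**The concern.** Scores taken before allocation cannot be affected by treatment. Their value in an arm comparison is to explain stable differences between patients. An independent t-test on follow-up scores leaves those differences in the error term and carries any chance imbalance at baseline into the arm contrast. Randomisation (section 6.2) is stratified only on mood-stabiliser use, so symptom severity may differ between arms by chance.

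This matters for hypothesis 2a, where the secondary objective is to estimate the effect of ImCT against psychoeducation, and section 1 wants first comparative data to inform a larger RCT. Four weekly scores, averaged, make a more reliable baseline than one score, and patients already supply them.

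**Working it through.** **The plan's own figure.** Section 4.4 gives 45 per arm for d = 0.6, two-sided 5%, 80% power. A noncentral-t calculation gives power 0.795 at 44 per arm and 0.804 at 45, so 45 is reproduced. With dropout of 1 in 15, 45 × (1 + 1/15) = 48, as stated; 45/(1 − 1/15) = 48.2 is close. That sizing is for the ALS-18. No power is stated for the weekly scales.

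**Inputs.** From the documents: k = 4 pre-allocation weeks, n = 45 evaluable per arm, two-sided 5%, 16 follow-up weeks. Assumed: a true difference of 0.5 SD and the correlation r between any two weekly scores. Bonferroni correction is not applied; it would lower every power below.

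**One post-randomisation week, equal correlation.** Variances are in units of one weekly score's variance. The four-week mean has variance B = (1 + 3r)/4.

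- Unadjusted score: 1
- Change from the four-week mean: 1 + B − 2r = 1.25(1 − r)
- Adjusted for the four-week mean: 1 − r²/B

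Power uses noncentrality (0.5/√variance) × √(45/2) with 88 degrees of freedom.

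| r | Unadjusted: variance, power | Change: variance, power | Adjusted: variance, power | Adjusted ÷ change |
|---|---|---|---|---|
| 0.4 | 1, 0.65 | 0.750, 0.77 | 0.709, 0.80 | 0.95 |
| 0.5 | 1, 0.65 | 0.625, 0.84 | 0.600, 0.86 | 0.96 |
| 0.6 | 1, 0.65 | 0.500, 0.91 | 0.486, 0.92 | 0.97 |

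Example at r = 0.5: B = 2.5/4 = 0.625, and 1 − 0.25/0.625 = 0.600.

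**Mean of the 16 follow-up weeks, equal correlation.** Unadjusted variance is (1 + 15r)/16, change is (1 − r)(1/16 + 1/4), and adjusted is the unadjusted value minus r²/B. At r = 0.4, 0.5 and 0.6, change gives 0.188, 0.156 and 0.125, and adjusted gives 0.147, 0.131 and 0.111. Adjustment cuts the variance of change by 22%, 16% and 11%.

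**Decaying correlation.** Let the correlation be s + (1 − s)a^lag, with s the stable share and a the weekly autoregression. For the last follow-up week:

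| s, a | Change ÷ unadjusted | Adjusted ÷ unadjusted | Adjusted ÷ change |
|---|---|---|---|
| 0.5, 0.5 | 0.76 | 0.67 | 0.88 |
| 0.4, 0.7 | 1.01 | 0.80 | 0.80 |
| 0.3, 0.8 | 1.24 | 0.89 | 0.72 |

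Here a change score can be worse than no adjustment, while adjustment still gains. If s is only 0.1–0.2 (a = 0.5–0.8, lags of 22–28 weeks), adjustment cuts the unadjusted variance by just 1–7%, and power is 0.66–0.68 against 0.65.

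**The case against.** The strongest reply is that the t-tests are post hoc. Section 8 first plans repeated-measures analyses of whether scores change more in one arm, which is most naturally a group-by-time contrast that already measures each patient against baseline. Against that, adjustment adds one to three points of power for a single week under equal correlation. This stands. It limits the size of the point but does not remove it: section 8 does not name the group-by-time term as deciding, it assigns the individual arm differences mostly to t-tests, and the gain over change grows with averaged weeks or decaying correlation.

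A reader might infer more than the documents support:

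- **That the pre-allocation weeks are certainly outcomes in the weekly model.** The whole-study weekly schedule and the listing of T0 and T1 in the parallel analysis suggest it, but section 8 does not say so. If only later weeks were meant, no baseline score would enter the comparison and the t-test loss would be the same.
- **That such weeks add only noise.** That is true of an arm main effect averaged over all weeks. In a group-by-time contrast they are the reference level and carry information.
- **That the plan forgoes 15 to 27 points of power.** That gap holds only against an unadjusted single-week t-test under the assumed correlations, and section 8 does not say whether its t-tests use raw or change scores.

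It is also fair to say that these are secondary outcomes in a feasibility trial and that no stated power figure is affected.

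**Conclusion.** The point holds as a matter of precision. No secondary arm comparison is adjusted for baseline, although four pre-allocation weekly scores per scale exist for QIDS-SR, BAI and ASRM. With 45 per arm, d = 0.5 and equal correlation of 0.4–0.6, adjustment removes 29–51% of single-week error variance relative to an unadjusted t-test, but about 3–5% relative to change from the four-week mean. The benefit over change is larger for averaged follow-up weeks or decaying correlation. The benefit over the unadjusted test is small if long-lag correlation is low. All of this rests on assumed correlations and an assumed effect. The ALS-18 sample size is untouched, and the planned comparisons are less efficient rather than invalid. The change is worth making because it costs almost nothing and is the more precise choice in every case examined.

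**What to change.** In section 8, for each weekly scale:

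1. State that only post-randomisation weeks are outcomes, and which weeks. This is needed anyway, because the arms have different numbers of weekly scores (4 + 12 + 16 = 32 for ImCT, 4 + 6 + 16 = 26 for psychoeducation).
2. Add the patient's mean pre-allocation weekly score on the same scale as a covariate.
3. Take the arm contrasts from this model in place of unadjusted t-tests, and name the deciding contrast.

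For secondary scales measured only at T0–T4, use T0 as the covariate. The mean of T0 and T1 is safe only once two sections are reconciled: 6.3.2 has T1 completed before allocation, whereas 9.2 lists allocation first. A T1 self-report given with knowledge of the arm should not be a baseline covariate.

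Apply the weekly fix to VAS-Imagery once its schedule is settled: section 2 confines imagery change to T0–T4, whereas section 6.1.2 has the VAS completed weekly in both arms.

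The cost is SAP wording and one degree of freedom per model, with no new data, patients or burden. The pre-allocation weekly scores cannot be influenced by knowledge of the arm.
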